## 10.7. Appendix 7: Kidney Safety: Monitoring Guidelines

### 10.7.1. Laboratory Assessment of Change in Kidney Function and Detection of Kidney Injury

Standard kidney safety monitoring requires assessment of baseline and postbaseline serum creatinine (SCr measurement to estimate glomerular filtration rate [SCr-based eGFR] or creatinine clearance [eCrCl]). Baseline and postbaseline serum Scys makes it feasible to distinguish AKI from other causes of SCr increase. If SCr increase is confirmed after baseline, then reflex measurement of Scys is indicated to estimate the combined SCr -Scys eGFR calculation (for adults only).

Regardless of whether kidney function monitoring tests are required as a routine safety monitoring procedure in the study, if the investigator or sponsor deems it necessary to further assess kidney safety and quantify kidney function, then these test results should be managed and followed per standard of care.

### 10.7.2. Age-Specific Kidney Function Calculation Recommendations

#### 10.7.2.1. Adults (18 Years and Above)—2021 CKD-EPI Equations

2021 CKD-EPI SCr Only	SCr (mg/dL)	Scys (mg/L)	Recommended eGFR Equation
Female	if $\leq 0.7$	N/A	$eGFR = 143 \times (SCr/0.7)^{-0.241} \times (0.9938)^{Age}$
Female	if $> 0.7$	N/A	$eGFR = 143 \times (SCr/0.7)^{-1.200} \times (0.9938)^{Age}$
Male	if $\leq 0.9$	N/A	$eGFR = 142 \times (SCr/0.9)^{-0.302} \times (0.9938)^{Age}$
Male	if $> 0.9$	N/A	$eGFR = 142 \times (SCr/0.9)^{-1.200} \times (0.9938)^{Age}$
2021 CKD-EPI SCr-Scys Combined	SCr (mg/dL)	Scys (mg/L)	Recommended eGFR Equation
Female	if $\leq 0.7$	if $\leq 0.8$	$eGFR = 130 \times (SCr/0.7)^{-0.219} \times (Scys/0.8)^{-0.323} \times (0.9961)^{Age}$
Female	if $\leq 0.7$	if $> 0.8$	$eGFR = 130 \times (SCr/0.7)^{-0.219} \times (Scys/0.8)^{-0.778} \times (0.9961)^{Age}$
Female	if $> 0.7$	if $\leq 0.8$	$eGFR = 130 \times (SCr/0.7)^{-0.544} \times (Scys/0.8)^{-0.323} \times (0.9961)^{Age}$
Female	if $> 0.7$	if $> 0.8$	$eGFR = 130 \times (SCr/0.7)^{-0.544} \times (Scys/0.8)^{-0.778} \times (0.9961)^{Age}$
Male	if $\leq 0.9$	if $\leq 0.8$	$eGFR = 135 \times (SCr/0.9)^{-0.144} \times (Scys/0.8)^{-0.323} \times (0.9961)^{Age}$
Male	if $\leq 0.9$	if $> 0.8$	$eGFR = 135 \times (SCr/0.9)^{-0.144} \times (Scys/0.8)^{-0.778} \times (0.9961)^{Age}$
Male	if $> 0.9$	if $\leq 0.8$	$eGFR = 135 \times (SCr/0.9)^{-0.544} \times (Scys/0.8)^{-0.323} \times (0.9961)^{Age}$
Male	if $> 0.9$	if $> 0.8$	$eGFR = 135 \times (SCr/0.9)^{-0.544} \times (Scys/0.8)^{-0.778} \times (0.9961)^{Age}$

Inker LA et al. N Engl J Med. 2021;385:1737-49.

### 10.7.3. Adverse Event Grading for Kidney Safety Laboratory Abnormalities

AE grading for decline in kidney function (ie, eGFR or eCrCl) will be according to KDIGO criteria.

## 10.8. Appendix 8: ECG Findings of Potential Clinical Concern

ECG Findings That May Qualify as AEs

Marked sinus bradycardia (rate <40 bpm) lasting minutes.

New PR interval prolongation >280 ms.

New prolongation of QTcF to >480 ms (absolute) or by <math>\geq 60</math> ms from baseline.

New-onset atrial flutter or fibrillation, with controlled ventricular response rate: ie, rate <120 bpm.

New-onset type I second-degree (Wenckebach) AV block of >30 seconds' duration.

Frequent PVCs, triplets, or short intervals (<30 seconds) of consecutive ventricular complexes.

ECG Findings That May Qualify as SAEs

QTcF prolongation >500 ms.

New ST-T changes suggestive of myocardial ischemia.

New-onset LBBB (QRS complex >120 ms).

New-onset right bundle branch block (QRS complex >120 ms).

Symptomatic bradycardia.

Asystole:

In awake, symptom-free participants in sinus rhythm, with documented periods of asystole <math>\geq 3.0</math> seconds or any escape rate <40 bpm, or with an escape rhythm that is below the AV node.

In awake, symptom-free participants with atrial fibrillation and bradycardia with 1 or more pauses of at least 5 seconds or longer.

Atrial flutter or fibrillation, with rapid ventricular response rate: rapid = rate >120 bpm.

Sustained supraventricular tachycardia (rate >120 bpm) ("sustained" = short duration with relevant symptoms or lasting >1 minute).

Ventricular rhythms >30 seconds' duration, including idioventricular rhythm (HR <40 bpm), accelerated idioventricular rhythm (HR >40 bpm to <100 bpm), and

monomorphic/polymorphic ventricular tachycardia (HR >100 bpm [such as torsades de pointes]).

- Type II second-degree (Mobitz II) AV block.
- Complete (third-degree) heart block.

#### **ECG Findings That Qualify as SAEs**

- Change in pattern suggestive of new myocardial infarction.
- Sustained ventricular tachyarrhythmias (>30 seconds' duration).
- Second- or third-degree AV block requiring pacemaker placement.
- Asystolic pauses requiring pacemaker placement.
- Atrial flutter or fibrillation with rapid ventricular response requiring cardioversion.
- Ventricular fibrillation/flutter.
- At the discretion of the investigator, any arrhythmia classified as an adverse experience.

The enumerated list of major events of potential clinical concern are recommended as “alerts” or notifications from the core ECG laboratory to the investigator and Pfizer study team, and not to be considered as all-inclusive of what to be reported as AEs/SAEs.

CCI

CCI

CCI

CCI

CCI

CCI

CCI

CCI

## 10.10. Appendix 10: Abbreviations

The following is a list of abbreviations that may be used in the protocol.

Abbreviation	Term
AA	alopecia areata
Abs	absolute
ADL	activity/activities of daily living
AE	adverse event
AKI	acute kidney injury
ALC	absolute lymphocyte count
ALT	alanine aminotransferase
ANC	absolute neutrophil count
AST	aspartate aminotransferase
ATE	arterial thromboembolism
AUC	area under the curve
AUC inf	area under the plasma concentration-time profile from time 0 extrapolated to infinite time
AUC last	area under the plasma concentration-time profile from time 0 to the time of the last quantifiable concentration
AV	atrioventricular
AxMP	auxiliary medicinal product
BA	bioavailability
BAEP	brainstem auditory evoked potential
β-hCG	β-human chorionic gonadotropin
BiC	Blend-in capsule
BID	twice a day
BMI	body mass index
BP	blood pressure
bpm	beats per minute
BUN	blood urea nitrogen
CD	Crohn's Disease
CFR	Code of Federal Regulations
CI	confidence interval
CIOMS	Council for International Organizations of Medical Sciences
CK	creatine kinase
CKD-EPI	chronic kidney disease epidemiology
CL/F	Apparent clearance after oral dose
C max	maximum observed concentration
CNS	central nervous system
CO 2	carbon dioxide (bicarbonate)
COVID-19	coronavirus disease 2019

Abbreviation	Term
CRF	case report form
CRO	contract research organization
CRU	clinical research unit
CSR	Clinical Study Report
CT	clinical trial
CTMS	clinical trial management system
CTIS	Clinical Trial Information System
DCT	data collection tool
DILI	drug-induced liver injury
EBV	Epstein Barr Virus
EC	ethics committee
ECC	emergency contact card
ECG	electrocardiogram or electrocardiography
eCrCl	estimated creatinine clearance
eCRF	electronic case report form
EDB	exposure during breastfeeding
E-DMC	External Data Monitoring Committee
EDP	exposure during pregnancy
EOT	End of treatment
EOI	event of interest
eGFR	estimated glomerular filtration rate
eSAE	electronic serious adverse event
EU	European Union
EudraCT	European Union Drug Regulating Authorities Clinical Trials (European Clinical Trials Database)
FSH	follicle stimulating hormone
F/U	follow-up
GCP	Good Clinical Practice
GGT	gamma-glutamyl transferase
HBcAb	hepatitis B core antibody
HBsAb	hepatitis B surface antibody
HBsAg	hepatitis B surface antigen
HCVAb	hepatitis C antibody
HIV	human immunodeficiency virus
HR	heart rate
HRT	hormone replacement therapy
HZ	herpes zoster
IB	Investigator's Brochure
ICD	informed consent document

Abbreviation	Term
ICH	International Council for Harmonisation of Technical Requirements for Pharmaceuticals for Human Use
ID	identification
IL	interleukin
IMI	Innovative Medicines Initiative
IMP	investigational medicinal product
IND	Investigational New Drug
INR	international normalized ratio
IP	investigational product
IPAL	Investigational Product Accountability Log
IPM	investigational product manual
IRB	Institutional Review Board
JAK	Janus kinase
KDIGO	Kidney Disease Improving Global Outcomes
$k_{el}$	first-order elimination rate constant
$t_{1/2}$	terminal phase half-life
LBBB	left bundle branch block
LFT	liver function test
MACE	Major Adverse Cardiac Events
MCH	mean corpuscular hemoglobin
MCHC	mean corpuscular hemoglobin concentration
MCV	mean corpuscular volume
MMR	measles, mumps, rubella
MQI	medically qualified individual
MTX-IR	inadequate response to MTX
NA	not applicable
NIMP	non-investigational medicinal product
NMSC	non-melanoma skin carcinoma
NOAEL	no-observed-adverse-effect level
PCRU	Pfizer Clinical Research Unit
PK	pharmacokinetic(s)
PNS	peripheral nervous system
PPD	purified protein derivative
PSSA	Pfizer's Serious Adverse Event Submission Assistant
PT	prothrombin time
PVC	premature ventricular contraction/complex
QD	Once a day
QFT-G	QuantiFERON®-TB Gold In-Tube
QTc	corrected QT interval
QTcF	QTc corrected using Fridericia's formula

Abbreviation	Term
QTL	quality tolerance limit
qual	qualitative
RA	rheumatoid arthritis
RBC	red blood cell
SAE	serious adverse event
SAP	Statistical Analysis Plan
SARS-CoV-2	severe acute respiratory syndrome coronavirus 2
SCr	serum creatinine
Scys	serum cystatin C
SoA	schedule of activities
SOC	system organ class
SOP	standard operating procedure
SRSD	Single Reference Safety Document
SUSAR	Suspected Unexpected Serious Adverse Reaction
TB	tuberculosis
T bili	total bilirubin
TEAE	treatment-emergent adverse events
TEC	tyrosine kinase expressed in hepatocellular carcinoma
THC	tetrahydrocannabinol
T max	time for maximum plasma concentration
TYK	tyrosine kinase
ULN	upper limit of normal
UC	ulcerative colitis
US	United States
WBC	white blood cell
WOCBP	woman/women of childbearing potential

## 1. VERSION HISTORY

**Table 1. Summary of Changes**

Version/ Date	Associated Protocol Amendment	Rationale	Specific Changes
1 / 27 Mar 2023	Original 02 Feb 2023	N/A	N/A

## 2. INTRODUCTION

*Ritlecitinib is a covalent and irreversible inhibitor of JAK3 with high selectivity over the other JAK isoforms (JAK1, JAK2, and TYK2). Ritlecitinib also inhibits irreversibly the TEC family kinases with selectivity over the broader human kinase. Treatment with ritlecitinib is expected to inhibit the inflammatory pathways mediated by IL 7, IL 15 and IL 21, all implicated in UC, CD, AA, RA, and vitiligo. Moreover, due to lack of activity against the other JAK isoforms, ritlecitinib is expected to spare immunoregulatory cytokines such as IL 10, IL 27 and IL 35, which are critical to the maintenance of immunosuppressive functions and immune homeostasis.*

*The objective of this study is to estimate the impact of administration methods on the bioavailability of the pediatric ritlecitinib blend-in capsule (BiC) formulation.*

This SAP provides the detailed methodology for summary and statistical analyses of the data collected in Study B7981078.

### 2.1. Modifications to the Analysis Plan Described in the Protocol

None.

### 2.2. Study Objectives and Endpoints

Objectives	Endpoints

Primary:
 
 
• To estimate the relative BA of ritlecitinib pediatric capsules (BiC) when sprinkled on food (apple sauce, strawberry jam, and yoghurt) compared to intact blend-in capsules (reference) at a 30 mg dose under fasted conditions in adult healthy participants.
 
• To estimate the effect of food on the relative BA of ritlecitinib pediatric capsules at a 30 mg dose.
 
	
Primary:
 
 
• Plasma AUCinf and Cmax of ritlecitinib.
 

Objectives	Endpoints
Secondary:	Secondary:

 
To evaluate the safety and tolerability of 30 mg BiCs of ritlecitinib administered to healthy adult participants under fasted and fed conditions.
 
	
 
AE monitoring.
 

Tertiary/Exploratory:	Tertiary/Exploratory:

 
To characterize the PK parameters for ritlecitinib (BiCs) when sprinkled on food (apple sauce, strawberry jam, and yoghurt) compared to intact BiC (reference)
 
Validate the PK measurement of ritlecitinib in capillary blood samples collected using microsampling device against the PK measurement of ritlecitinib in venous blood samples.
 
To assess the sensory characteristics and overall palatability of sprinkled BiC by healthy participants.
 
	
 
<math>T_{max}</math>, <math>AUC_{inf}</math>, <math>t_{1/2}</math>, (if data permit) and other PK parameters such as <math>CL/F</math>, <math>V_z/F</math>.
 
Ritlecitinib microsampling concentration versus plasma concentrations from venous blood samples.
 
• CCI [REDACTED]
 

### 2.3. Study Design

The study will be conducted as a Phase 1, open-label, single dose, randomized 4-crossover periods and 1-fixed period design in a single cohort of approximately 12 healthy male or female participants at a single center. Participants will be randomized into 1 of 4 sequences of treatment as described in Table 2.

**Table 2. Study Design and Treatments**

Treatment Sequence	Period 1	Period 2	Period 3	Period 4	Period 5 (fixed period)
1 (n=3)	A	B	C	D	E
2 (n=3)	B	D	A	C	E
3 (n=3)	C	A	D	B	E
4 (n=3)	D	C	B	A	E

Abbreviations: *n* = number of participants.

Treatment A: ritlecitinib 1 x 30 mg pediatric capsule in fasted state

Treatment B: contents of ritlecitinib 1 x 30 mg pediatric capsule sprinkled on strawberry jam in fasted state

Treatment C: contents of ritlecitinib 1 x 30 mg pediatric capsule sprinkled on yoghurt in fasted state

**Table 2. Study Design and Treatments**

*Treatment D: contents of ritlecitinib 1 x 30 mg pediatric capsule sprinkled on applesauce in fasted state  
Treatment E: ritlecitinib 1 x 30 mg pediatric capsule given with high fat meal*

*Since ritlecitinib is rapidly eliminated ( $t_{1/2} \sim 2$  hours), there will be at least a 48-hour washout between each dose.*

**3. ENDPOINTS AND BASELINE VARIABLES: DEFINITIONS AND CONVENTIONS**

**3.1. Primary Endpoints**

The primary endpoints are the plasma  $AUC_{inf}$  (if data permit, otherwise  $AUC_{last}$ ) and  $C_{max}$  of ritlecitinib. The test/reference ratios for  $AUC_{inf}$  (if data permit),  $AUC_{last}$  and  $C_{max}$  will be derived with Treatments B, C, and D (pediatric capsules sprinkled in strawberry jam, pediatric capsules sprinkled in yoghurt, and pediatric capsules sprinkled in applesauce, respectively) as the test treatments and Treatment A (pediatric capsules) as the reference treatment. In addition, the test/reference ratios for  $AUC_{inf}$  (if data permit),  $AUC_{last}$  and  $C_{max}$  will be derived with Treatment E (pediatric capsules given with high fat meal) as the test treatment and Treatment A (pediatric capsules) as the reference treatment.

*PK parameters following a single dose administration will be derived from the concentration-time profiles using noncompartmental methods as data permit. The various PK parameters to be assessed in this study, their definition, and method of determination are outlined in Table 3. In all cases, actual PK sampling times will be used in the derivation of PK parameters.*

**Table 3. Definitions of PK Parameters**

Parameter	Definition	Method of Determination
$AUC_{last}$	Area under the plasma concentration-time profile from time zero to the time of the last quantifiable concentration (<math>C_{last}</math>)	Linear-log trapezoidal method
$AUC_{inf}$	Area under the plasma concentration-time profile from time zero extrapolated to infinite time	$AUC_{last} + (C_{last}/k_{el})$ where $C_{last}$ is the predicted plasma concentration at the last quantifiable time point estimated from the log-linear regression analysis
$C_{max}$	Maximum plasma concentration	Observed directly from the data
$T_{max}$	Time for <math>C_{max}</math>	Observed directly from the data as time of first occurrence
$t_{1/2}$	Terminal elimination half-life	$\log_2(2)/k_{el}$ Only those data points judged to describe the terminal log-linear decline will be used in the regression.
$CL/F$	Apparent clearance after oral dose	$Dose/AUC_{inf}$ after oral dose
$V_z/F$	Apparent volume of distribution after oral dose	$Dose/(AUC_{inf} \cdot k_{el})$ after oral dose

### 3.2. Secondary Endpoints

The secondary endpoints are the safety and tolerability data, discussed in [Section 3.5](#).

### 3.3. Baseline Variables

Baseline characteristics will be collected according to the schedule of activities (SoA) as specified in the protocol.

### 3.4. Other Endpoints

#### 3.4.1. Other PK parameters for ritlecitinib

Exploratory endpoints include other PK parameters for ritlecitinib such as  $T_{max}$ ,  $t_{1/2}$ ,  $CL/F$  and  $V_z/F$ .

#### 3.4.2. Ritlecitinib microsampling concentration

Ritlecitinib microsampling concentration using Tasso device will be collected according to the SoA as specified in the protocol.

#### 3.4.3. Palatability of sprinkled ritlecitinib BiC

CCI

CCI

### **3.5. Safety Endpoints**

The following data are considered in standard safety summaries (see protocol for collection days, baseline assessment, and list of parameters):

- adverse events (AE)
- laboratory data
- vital signs data
- electrocardiogram (ECG) results

#### **3.5.1. Adverse Events**

Any adverse events occurring following start of treatment will be considered as treatment emergent adverse event (TEAE). Events that occur during follow-up within the lag time of up to 35 days after the last dose of study intervention will be counted as treatment emergent and attributed to the last treatment taken. The time period for collecting AEs (“active collection period”) for each participant begins from the time the participant provides informed consent.

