**Table 1. Study Schedule of Assessment**

Visit Identifier Abbreviations used in this table may be found in Appendix 10 .	Screen	Treatment Period												Notes	
		Period 1		Period 2		Period 3		Period 4		Period 5		F/U	Early Discont		
Days Relative to Day 1	Day -28 to Day -2	Day -1	Day 1	Day 2	Day 1	Day 2	Telephone Contact								
Study Day	-28 to -2	-1	1	2	3	4	5	6	7	8	9	10	37 to 44		
Informed consent	X														
CRU confinement		X	→	→	→	→	→	→	→	→	→	X			• The participants will be discharged on Day 2 of Period 5.
Inclusion/exclusion criteria	X	X													• Inclusion/exclusion criteria should be updated on Day -1 since screening.
Demographic information	X														• Including measurement of height and weight
Medical/medication, drug, tobacco and alcohol history	X	X													• Include history of alcohol abuse, tobacco/nicotine containing products, licit and illicit drug use or dependence within 6 months of Screening. For Day -1, records should be reviewed or updated only.
Complete/ brief physical examination	X	X													• Complete (full) physical examination must either be conducted at Screening or upon Admission on Day -1 only; targeted physical examination may be performed as appropriate at discharge/early termination/discontinuation

PFIZER CONFIDENTIAL

CT02-GSOP Clinical Pharmacology Protocol Template (01 April 2022)

Page 16

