### 3. OBJECTIVES AND ENDPOINTS

Objectives	Endpoints
Primary:	Primary:

 
To estimate the relative BA of ritlecitinib BiC when sprinkled on food (apple sauce, strawberry jam, and yoghurt) compared to intact BiC (reference) at a 30 mg dose under fasted conditions in adult healthy participants.
 
To estimate the effect of food on the relative BA of ritlecitinib intact BiCs at a 30 mg dose.
 
	
 
Plasma <math>AUC_{inf}</math> and <math>C_{max}</math> of ritlecitinib.
 

Secondary:	Secondary:

 
To evaluate the safety and tolerability of 30 mg BiCs of ritlecitinib administered to healthy adult participants under fasted and fed conditions.
 
	
 
S AE monitoring.
 

Tertiary/Exploratory:	Tertiary/Exploratory:

 
To characterize the PK parameters for ritlecitinib (BiCs) when sprinkled on food (apple sauce, strawberry jam, and yoghurt) compared to intact BiC (reference).
 
Validate the PK measurement of ritlecitinib in capillary blood samples collected using micro-sampling device against the PK measurement of ritlecitinib in venous blood samples.
 
To assess the sensory characteristics and overall palatability of sprinkled BiC by healthy participants.
 
	
 
<math>T_{max}</math>, <math>AUC_{inf}</math>, <math>t_{1/2}</math> (if data permit) and other PK parameters such as CL/F, <math>V_z/F</math>.
 
Ritlecitinib microsampling concentration versus plasma concentrations from venous blood samples.
 
CC1
 

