**Table 3. Study Design and Treatments**

Treatment Sequence	Period 1	Period 2	Period 3	Period 4	Period 5 (fixed period)
1 (n=3)	A	B	C	D	E
2 (n=3)	B	D	A	C	E
3 (n=3)	C	A	D	B	E
4 (n=3)	D	C	B	A	E

Abbreviations: n = number of participants.

Treatment A: ritlecitinib 1 x 30 mg intact BiC in fasted state

Treatment B: contents of ritlecitinib 1 x 30 mg BiC sprinkled on strawberry jam in fasted state

Treatment C: contents of ritlecitinib 1 x 30 mg BiC sprinkled on yoghurt in fasted state

Treatment D: contents of ritlecitinib 1 x 30 mg BiC sprinkled on applesauce in fasted state

Treatment E: ritlecitinib 1 x 30 mg intact BiC given with high fat meal

Since ritlecitinib is rapidly eliminated ( $t_{1/2} \sim 2$  hours), there will be at least a 48-hour washout between each dose.

Blood samples for PK analysis will be collected pre-dose and at 0.25, 0.5, 1, 1.5, 2, 3, 4, 6, 9, 12, and 24 hours postdose. Serial blood samples (normal venous PK blood samples as well as capillary blood samples using micro-sampling Tasso device) at specified intervals as per [SoA](#) ([Table 2](#)) will be collected for 24 hours postdose for PK assessments (Treatment A).

CCI

Participants will participate in the study up to approximately 2.5 months, with the inclusion of the screening and follow-up period. Participants will be screened within 28 days of the first dose of study intervention and if all entry criteria are fulfilled, the participants will report to the CRU on the day prior to Day 1 dosing (Day 1). On Day 1 of each period, participants will receive a single dose of IP. Administration of IP will be via dosing using intact BiCs with water or by emptying the capsule contents on soft food as per dosing instructions. Participants assigned to receive IP under fasted conditions must be fasted for at least 10 hours predosing and 4 hours postdosing.

Participants will be confined in the CRU for a total of at least 11 days and discharged at the discretion of the investigator. A follow-up phone call will be made at least 28 calendar days and up to 35 calendar days after the last administration of the study intervention to capture any potential AE and confirm appropriate contraceptive usage.

PFIZER CONFIDENTIAL

CT02-GSOP Clinical Pharmacology Protocol Template (01 April 2022)

Page 31

Tolerability and safety will be assessed for all treatments by monitoring adverse events.

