### 6.1.1. Administration

For **fasted** periods:

- Following an overnight fast of at least 10 hours, the participants will receive study intervention at approximately 08:00 hours (plus or minus 2 hours) without breakfast/standard meal on Day 1.

For **fed** period:

- Following an overnight fast of at least 10 hours, participants will receive breakfast approximately 30 minutes prior to dosing which is to be completed within approximately 20 minutes as outlined in [Section 5.3.2](#) (Meals and Dietary Restrictions). The participants will then receive study intervention at approximately 08:00 hours (plus or minus 2 hours).
- The participants will then receive study intervention at approximately 08:00 hours (plus or minus 2 hours). PF-06651600 should be administered within approximately 10 minutes of completion of the meal.

For **all** periods:

- Investigator site personnel will administer study intervention during each period with ambient temperature water to a total volume of approximately 240 mL. For treatments A and E only: Participants will swallow the study intervention whole, and will not manipulate or chew the study intervention prior to swallowing. Administer study intervention according to the IP Manual.

- In order to standardize the conditions on PK sampling days, all participants will be required to refrain from lying down (except when required for BP, pulse rate, and ECG measurements), eating, and drinking beverages other than water during the first 4 hours after dosing.

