#### 4. ANALYSIS SETS (POPULATIONS FOR ANALYSIS)

Data for all participants will be assessed to determine if participants meet the criteria for inclusion in each analysis population prior to releasing the database and classifications will be documented per standard operating procedures.

Participant Analysis Set	Description
Safety Analysis Set	All participants randomly assigned to study intervention and who take at least 1 dose of study intervention. Participants will be analyzed according to the product they actually received.
PK Concentration Set	The PK concentration population is defined as all participants randomized and treated who have at least one concentration in at least 1 treatment period.
PK Parameter Set	The PK parameter analysis population is defined as all participants randomized and treated who have at least 1 of the PK parameters of primary interest in at least 1 treatment period.

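### SAP 3.5.1 gives Treatment E a 28–35 day adverse-event window against a scheduled 2 days for each fasted treatment, so any by-treatment AE counts would not be comparable

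*SAP*

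**What the plan says.** SAP 3.5.1 treats any adverse event after the start of treatment as treatment emergent. Events in follow-up, up to 35 days after the last dose, "will be counted as treatment emergent and attributed to the last treatment taken". The section gives no rule for assigning events that begin between doses.

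The design tables (Protocol 4.1, Table 3; SAP 2.3, Table 2) place E in Period 5 of every sequence. E is the intact capsule with a high-fat meal; A–D are all given fasted.

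On timing, Protocol 4.1 states that "there will be at least a 48-hour washout between each dose", and then: "A follow-up phone call will be made at least 28 calendar days and up to 35 calendar days after the last administration". The Schedule of Activities (Protocol 1.3, Table 1) puts dosing on Study Days 1, 3, 5, 7 and 9 and the telephone contact on Days 37 to 44. It notes: "The participants will be discharged on Day 2 of Period 5", which is Study Day 10.

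The text on AE display is thin. SAP 6.6.1 defers to the sponsor's reporting standard (CaPS) and specifies a by-treatment presentation only for discontinuations due to AEs. Other text points towards by-treatment tables. Protocol 4.1 says "Tolerability and safety will be assessed for all treatments by monitoring adverse events", and SAP 4 says of the safety set: "Participants will be analyzed according to the product they actually received". The secondary objective (Protocol 3) covers safety and tolerability of the 30 mg capsules "administered to healthy adult participants under fasted and fed conditions", with AE monitoring as its only endpoint.

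**The concern.** Assigning follow-up events to the last treatment does little harm when the last treatment rotates across sequences. Over Periods 1–4 it would rotate: Period 4 is D, C, B and A, once each. The fixed fifth period removes that balance. Every completer's month of follow-up goes to one treatment, and that treatment is the only fed one.

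A reader who compared the E column of an AE table with the A–D columns would be comparing about a month of attributable time with about two days. With roughly 12 participants, a few unrelated events after discharge could make the fed condition look worse. Poor recall at the phone call could hide events instead. Either way, the columns would not describe fed and fasted tolerability on the same footing, and AE monitoring is all that the secondary objective has.

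**Working it through.** **Reproducing the plan's figure.** E is dosed on Study Day 9. 9 + 28 = 37 and 9 + 35 = 44, which matches the contact window in the Schedule of Activities.

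**Calendar windows per completer.** The gaps between doses on Days 1, 3, 5, 7 and 9 are 2 days each.

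| Quantity | Calculation | Result |
|---|---|---|
| Each of A–D | next dose minus dose | 2 days |
| A–D pooled | 4 × 2 | 8 days |
| E | Day 9 to Day 37–44 | 28–35 days |
| E against one fasted treatment | 28/2 to 35/2 | 14 to 17.5 |
| E against A–D pooled | 28/8 to 35/8 | 3.5 to 4.4 |
| E's share of attributable time | 28/36 to 35/43 | 78% to 81% |

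In person-days for 12 completers, E has 12 × 28 = 336 to 12 × 35 = 420, and each of A–D has 12 × 2 = 24.

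**Sensitivity to the 2-day figure.** The 48 hours is a minimum.
- If the Study Days are kept, Protocol 6.1.1 (fasted periods) still allows some drift: "the participants will receive study intervention at approximately 08:00 hours (plus or minus 2 hours) without breakfast/standard meal on Day 1". The fed period has the same clock window. The band is 4 hours wide, so one interval can reach at most 52 hours, or 2.167 days. The ratio is then 28/2.167 = 12.9 to 35/2.167 = 16.2.
- If an interval ran to 3 days, the ratio against that treatment would be 28/3 = 9.3 to 35/3 = 11.7.

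**Early stopping.** If one of 12 stops after a fasted treatment, the long window moves to that treatment: 11 × 2 + 28 = 50 to 11 × 2 + 35 = 57 person-days instead of 24.

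**From windows to counts.** This step needs inputs that the documents do not give. Assume the same daily AE rate in the unit for every treatment, and recording after discharge at a fraction f of that rate. On the schedule, E has about 1 day in the unit and 27–34 days after discharge. The expected ratio of E to one fasted treatment is then (1 + 27f)/2 to (1 + 34f)/2.

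| f | Ratio |
|---|---|
| 0 | 0.5 |
| 0.1 | 1.9 to 2.2 |
| 0.25 | 3.9 to 4.8 |
| 0.5 | 7.3 to 9 |
| 1 | 14 to 17.5 |

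The ratio equals 1 at f = 1/27 = 0.037 or f = 1/34 = 0.029. Below that, E is under-counted; above it, E is over-counted. If AEs cluster on the dosing day, the ratio at f = 0 is nearer 1 than 0.5. The table shows how far the result depends on f; it is not an estimate of harm.

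**The case against.** The attribution rule is stated openly, and it feeds a table that we cannot see. CaPS may already provide a follow-up column, and SAP 6.6.1 promises a by-treatment display only for AE discontinuations. This stands as a limit on certainty. Still, attributing an event to a treatment has little purpose unless events are shown by treatment. The safety-set wording and the by-treatment laboratory summary (SAP 6.6.2) point the same way.

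The objective is to evaluate safety under both conditions, not to test fed against fasted. SAP 5.1 tests no hypothesis, all five treatments are the same drug at the same dose, and investigators weigh timing when they judge causality (Protocol 10.3.3). All of this is right and confines the matter to presentation. Causality judgements do not repair all-causality counts, which ignore them.

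A reader might infer that E's AE counts will be inflated 14- to 17.5-fold. The documents do not support that. Those figures are calendar time, and nothing in the plan fixes how completely events after discharge are recorded. The phone call is the one scheduled contact, although spontaneously reported events are also recorded (Protocol 8.4.1.2). Discharge is at the investigator's discretion after at least 11 days of confinement (Protocol 4.1), so E's time in the unit may exceed 1 day.

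A reader might also infer that a 48-hour window for every treatment would settle the matter. It would not: for A–D all 48 hours fall in the unit, but for E the second 24 hours fall after the scheduled discharge. Nor does any rewording give a clean fed-versus-fasted AE comparison, because E is always fifth and so is confounded with period and prior doses.

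**Conclusion.** The imbalance in attributable time is established from the schedule and the rule in SAP 3.5.1, on the assumption that the scheduled Study Days are kept and the participant completes all five periods. The consequence is conditional: if AEs are tabulated by treatment, raw counts for E and for A–D do not share a common basis. The effect on counts is unknown in both size and direction.

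This is a reporting weakness in a descriptive secondary endpoint. It does not touch the AUC or Cmax analyses or any decision rule. It merits a cheap improvement to the SAP and does not call the design into question. Confidence is medium, because the table layout is inferred.

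**What to change.** In SAP 3.5.1 and 6.6.1, for any by-treatment AE table:

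- Show events with onset after discharge from the unit in a separate follow-up column, footnoted with the last treatment taken. For a participant who stops early, apply the same to events after the last period in which they were dosed.
- Keep every treatment-emergent event in the overall total.
- Footnote the length of each treatment's window.
- If a common window is wanted, use 24 hours after dosing. Under the schedule this lies within the unit for all five treatments.

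The cost is SAP wording and one table column. No new data are needed, no events are lost, and the table of discontinuations due to AEs need not change.

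There are two downsides. Late events no longer appear under a treatment column. Without the 24-hour window, E's time in the unit (about 1 day) is shorter than that of each fasted treatment (about 2 days), so the window footnote is still needed. With it, events in the second day after A–D also move out of the treatment columns. The confounding of E with period remains.
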